The PROACT trial will evaluate the value of providing proactive support to current smokers as part of participating in lung cancer screening including behavioral and pharmacotherapy support. Cessation support guidelines have emphasized the importance of providing both behavioral and pharmacotherapy support at every opportunity. Cessation support will be integrated with the reporting of screening results. In our pilot study of the proactive telephone counseling component of the proposed intervention, we increased participation in behavioral cessation treatment to 44% among participants who received proactive counseling from 11% among control patients who did not receive proactive counseling, and quit rates more than doubled to 19% in the proactive group from 7% in the control group.⁸ Screening patients often report being motivated to participate in screening to find out how much smoking has harmed them.⁶ The proactive care activities are designed to convert this level of patient engagement into an opportunity to encourage cessation. Integrating the proactive cessation treatment approach into the screening process ensures that all screening patients are offered cessation support by default, and removes the precondition of providing pharmacotherapy support only to patients who agree to set a specific quit date. Over 14 trials⁹ have shown that providing pharmacotherapy support to all current smokers using an opt-out approach (rather than requiring patients to request treatment) significantly increases quit rates, and providers have begun adopting opt-out approaches to offering tobacco treatment.

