The difference in risks associated with behavioral counseling between the unstructured and proactive arms are minor. In the unstructured arm, patients receive about cessation counseling by their provider and are provided with the VA Quitline's telephone number ([name]) as a free resource for telephone counseling. In the proactive arm, subjects are proactively contacted by telephone counselors to receive this same support. The proactive counseling calls may be associated with the following risks: 1) annoyance from proactive counseling outreach, or 2) increased anxiety or worry related to discussions around lung cancer screening results and smoking cessation with VA Quitline telephone counselors. We will mitigate this risk by having the VA Quitline caller remind subjects that participation in the proactive calls is voluntary. Notably, in the pilot study 89% of Veterans indicated they were completely or somewhat satisfied with the proactive telephone counseling calls, with 1 individual reporting they were neither satisfied or dissatisfied, and 2 participants declining to respond.

The difference in risks associated with pharmacotherapy support between the unstructured and proactive arms is also minimal. Although guidelines indicate all smokers should be offered pharmacotherapy support at every visit, this happens infrequently. A recent review found that only 7.6% of current smokers received a cessation pharmacotherapy order

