following a primary care visit,¹⁸ and fewer than 10% of smokers participating in screening in the NLST received such an order.¹⁷ Patients who are current smokers should be appropriately provided with smoking cessation support as they participate in lung cancer screening, although this doesn't consistently happen. A potential risk of this study is that current smokers receiving care from providers in the unstructured care group who are eligible for behavioral counseling or pharmacologic cessation support will not receive it. Another potential risk is that providers in the proactive care group will perceive that the study is assuming responsibility for providing cessation support and the quality of support offered by providers will decrease. The primary difference between the study arms is encouraging providers assigned to proactive care to remove the precondition to providing pharmacotherapy that the patient set a quit date and offer pharmacotherapy to all screening participants who are current smokers. This is intended to result in more patients in the proactive care arm receiving pharmacotherapy and may be associated with 1) inappropriate use of cessation medications, or 2) risks associated with use of cessation medications. We will encourage providers to follow VHA formulary guidelines for recommending pharmacotherapy including assessment of contraindications, and all orders are required to be signed by a primary care provider associated with the patient. The local coordinator will review patients' medication history as well as any potential medication risk factors and provide a note in CPRS with a summary for the provider to assist in assessing potential contraindications and facilitating adherence to VHA formulary guidelines.

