Secondary outcome	Use of smoking cessation support within 3 months of LCS	Indicator for receipt of medication or behavioral counseling	Binary treatment indicator; Binary site indicator; Categorical provider (clustering variable)	Logistic regression with random intercept for provider	
Secondary outcome	Use of smoking cessation support within 12 months of LCS	Indicator for receipt of medication or behavioral counseling	Binary treatment indicator; Binary site indicator; Categorical provider (clustering variable)	Logistic regression with random intercept for provider	
Secondary outcome	Smoked in the last 7 days (3 month survey)	Indicator for smoking	Binary treatment indicator; Binary site indicator; Categorical provider (clustering variable)	Logistic regression with random intercept for provider	
Secondary outcome	Smoked in the last 7 days (12 month survey)	Indicator for smoking	Binary treatment indicator; Binary site indicator; Categorical provider (clustering variable)	Logistic regression with random intercept for provider	
Secondary outcome	Quit attempts since LCS (3 months)				
Secondary outcome	Tried to reduce or cutdown	Indicator for Yes	Binary treatment indicator;	Logistic regression with	

Analysis	Description	Outcome	Independent Variable(s)	Model type	Statistical Test
	since LCS (3 months		Binary site indicator; Categorical provider (clustering variable)	random intercept for provider	
Secondary outcome	Quit attempts since LCS (12 months)				
Secondary outcome	Tried to reduce or cutdown since LCS (12 months	Indicator for Yes	Binary treatment indicator; Binary site indicator; Categorical provider (clustering variable)	Logistic regression with random intercept for provider	
Secondary outcome	Support Satisfaction	Ordered categorical (A little/not at all satisfied, somewhat satisfied, very satisfied)	Binary treatment indicator; Binary site indicator; Categorical provider (clustering variable)	Ordered logistic regression with random intercept for provider	
Secondary outcome	Motivation to quit	Score on motivation to quit scale	Binary treatment indicator; Binary site indicator; Categorical provider (clustering variable)	Linear regression with random intercept for provider	
Secondary outcome	Self-efficacy for quitting	Score on self-efficacy scale	Binary treatment indicator; Binary site indicator; Categorical provider	Linear regression with random intercept for provider	

Analysis	Description	Outcome	Independent Variable(s)	Model type	Statistical Test

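### Support Satisfaction is compared between arms on a scale with no level for patients who had no support, and the SAP does not say who is analysed; if only recipients rate it, the comparison is not a randomized one

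*SAP*

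**What the plan says.** The analysis table in SAP section 7 lists Support Satisfaction as a secondary outcome. Its levels are "Ordered categorical (A little/not at all satisfied, somewhat satisfied, very satisfied" and its model is "Ordered logistic regression with random intercept for provider", with treatment and site as predictors. The row gives no analysis set, no survey timepoint, no definition of support and no rule for patients who had none.

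Other text does not fill the gap:

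- The outcome table in SAP section 5 has no Support Satisfaction entry. The nearest one, experience with telephone counseling at 3 months, is binary.
- SAP section 8 sets a complete-case rule for the primary outcome only.
- The intent-to-treat text in Protocol section 5.6 gives no rule for this outcome.

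The same SAP table makes use of cessation support a separate outcome at 3 and 12 months, defined as "Indicator for receipt of medication or behavioral counseling". The protocol expects the arms to differ on it. Its opening summary reports that the pilot "increased participation in behavioral cessation treatment to 44% among participants who received proactive counseling from 11% among control patients". Of offering medication without requiring a quit date, Protocol section 5.1 says: "This is intended to result in more patients in the proactive care arm receiving pharmacotherapy".

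**The concern.** A satisfaction rating normally presupposes that something was received. If patients without support give no rating, the model compares recipients in one arm with recipients in the other. Being a recipient is determined after randomization, and the intervention exists to change it. Proactive-arm recipients would include patients who were telephoned without asking. The unstructured-arm group would be formed by a different process. Randomization does not balance the two groups, and the treatment coefficient would mix how good the support was with who ended up receiving it.

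Placing non-recipients in the lowest level keeps everyone in but changes the question: the arm with more recipients looks more satisfied because of uptake. The two codings can push the odds ratio in opposite directions, and the SAP does not choose between them. What is at stake is whether the report can say that patients liked proactive care more, or less, than usual care.

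**Working it through.** The documents give no expected value, sample size or power for this outcome, so there is no planned figure to reproduce. The check asks what the comparison would estimate under each reading of the row.

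**Inputs from the documents.** Pilot participation in behavioral treatment is 44% proactive and 11% control (Protocol opening summary). The target is 270 respondents per arm (Protocol section 5.6). That target belongs to the 12-month survey; the satisfaction row names no survey.

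**Assumptions not in the documents.** If every smoker were rated, satisfaction would split 25% / 35% / 40% from lowest to highest level. Arm has no effect on satisfaction. Satisfaction and the propensity to use support are jointly normal with correlation ρ, and the patients with the highest propensity are the users.

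**Step 1: raters if only counseling users answer.**
- Proactive: 0.44 × 270 = 118.8, about 119.
- Unstructured: 0.11 × 270 = 29.7, about 30.

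The pilot tested only the telephone counseling component. Medication-only users would add to both counts by an amount the documents do not give.

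**Step 2: recipients only, no true arm effect** (2 million simulated patients). OR = [p₁/(1−p₁)] / [p₀/(1−p₀)], proactive over unstructured.

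| ρ | Very satisfied, proactive | Very satisfied, unstructured | OR, very | OR, somewhat or very |
|---|---|---|---|---|
| 0 | 40.1% | 40.1% | 1.00 | 1.00 |
| 0.2 | 47.0% | 53.6% | 0.77 | 0.74 |
| 0.3 | 50.6% | 60.8% | 0.66 | 0.61 |
| 0.5 | 58.2% | 74.9% | 0.47 | 0.36 |

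For example, at ρ = 0.3: (0.506/0.494) / (0.608/0.392) = 0.66. The documents give no value for ρ. At ρ = 0 there is no bias, and a negative ρ would push the odds ratio above 1.

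**Step 3: non-recipients in the lowest level, recipients equally satisfied (25/35/40) in both arms.**
- Very satisfied: 0.44 × 0.40 = 0.176 against 0.11 × 0.40 = 0.044. OR = (0.176/0.824) / (0.044/0.956) = 4.6.
- Somewhat or very: 0.44 × 0.75 = 0.330 against 0.11 × 0.75 = 0.0825. OR = (0.330/0.670) / (0.0825/0.9175) = 5.5.

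Both odds ratios come from uptake alone.

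**Step 4: broad reading of support.** If the item covers provider counseling at screening, most patients in both arms may have something to rate. The bias in Step 2 then shrinks by an amount that cannot be computed from the documents.

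**The case against.** The strongest reply is that the restriction to recipients is inferred. The SAP never states it, and the patient survey, an appendix to the protocol, is not in the supplied text. If the item asks about support offered by VA, a patient who got little or nothing could choose the lowest level. This stands, so the point must be conditional. A reader might infer that the plan definitely compares self-selected users; the documents do not say so.

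A reader might also infer that unstructured-arm raters would be only the few who sought help. Protocol section 5.1 does not support that: "In the unstructured arm, patients receive about cessation counseling by their provider", along with the Quitline number. Section 2.0 puts VA primary care adherence to cessation guidelines, including the 5A's, above 80%. Under a broad definition of support, self-selection is smaller. It remains true that support is undefined for this row, while the same table defines use of support as medication or behavioral counseling.

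A third tempting step is to say that 540 − 149 = 391 respondents (72%) would be excluded. That treats telephone-counseling pilot rates as the rate of receiving any support, and borrows a 12-month target for an outcome with no timepoint. The pilot supports an expected difference in uptake, not this count.

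Finally, the SAP already compares use of support by arm and promises to examine differential missingness in outcomes. That would show unequal denominators but would not remove selection from the satisfaction odds ratio.

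**Conclusion.** The point holds in conditional form. It is certain that the scale has no level for no support, and that the SAP leaves the analysis set and the coding of non-recipients open. If only recipients rate support, which is the most natural reading, the treatment odds ratio is not a randomized comparison. Under the stated assumptions it runs from 1.00 to 0.47 for very satisfied as ρ goes from 0 to 0.5, with no true effect. If non-recipients take the lowest level, it is 4.6 from uptake alone. These values show direction and possible size; they do not predict this trial's result. They rest on an assumed satisfaction split, an assumed ρ and pilot counseling rates without medication-only users.

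The matter is minor. Patient satisfaction with support is not among the aims in Protocol section 3.0, where aim 2b concerns providers. A reader should not carry the concern over to the 12-month abstinence result, which uses a different outcome and is unaffected.

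**What to change.** Change the Support Satisfaction row in SAP section 7 to a descriptive summary by arm among patients who received support. Give the number of recipients in each arm, fit no between-arm test, and label the summary as a non-randomized comparison. State in the row what counts as support, which survey supplies the rating, and how patients without support are recorded.

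If a randomized comparison is wanted, analyse all survey respondents with one binary outcome: received support and was somewhat or very satisfied. The random-intercept logistic model used for the table's other binary outcomes will serve. Label the result as combining uptake and satisfaction. It will largely follow the use-of-support outcomes already in the table and should not be read as satisfaction alone.

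The cost is a wording change to one row and the loss of one secondary p-value.

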5.2 Recruitment Methods

Number of Subjects Needed.

Patients. We will assess CDW and CAPRI/JLV records for up to 15,000 patients (~10,000 to identify retrospective LCS orders, and ~5,000 to identify prospective LCS orders) who were offered lung cancer screening at NY Harbor and Providence to identify potential provider participants. Of these subjects, only current smokers will be approached. We anticipate approaching up to 1,350 eligible potential subjects (mailing them a study invitation packet) to invite them to participate in the survey. In order to ensure non-missing data are available on a sufficiently powered study sample, recruitment will continue until 270 subjects have completed the 12-month assessment survey in each of the care arms (total target n = 540).

Providers. We expect to recruit approximately 300 providers, 180 from Providence, RI and 120 from NY Harbor, in order to reach 540 patients (completed surveys).

Identification and Recruitment of Subjects.

Providers. We will obtain a Waiver of Informed Consent for recruitment to facilitate the identification of primary care providers ordering LCS CT scans at the NY Harbor and Providence VAs. At the beginning of the study, the study team will examine historical CDW data to identify providers who have previously ordered LCS tests. Providers who meet eligibility will then be contacted via mail, then email, and finally by Lync/Skype for Business instant message and given the recruitment materials. Any new providers who are hired at VA NY Harbor or Providence and are eligible to order a LCS CT scan, who were not identified by the historical review, will be similarly recruited when they are first identified.

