5.6 Data Analysis

Sample size determination. Our target sample size of 270 respondents per arm with complete 12-month outcome information was selected to have sufficient (80%) power to detect a doubling of abstinence rates (Relative Risk = 2) using a multilevel random effects model with patients clustered by randomized provider. The assumed intraclass correlation coefficient for the provider clustering effect is assumed to be 0.01. Power is based on a two-sided test with type-1 alpha error rate of 0.05%. Due to randomization, we do not anticipate needing to adjust for patient covariates.

Intent-to-treat (ITT) analysis We will utilize an intent-to-treat approach and include all participants who meet study eligibility criteria and are assigned to a study arm, regardless of whether they participated in all of the care components of that arm (e.g. declined proactive telephone counseling). Our primary analysis will focus on participants for whom we have complete 12-month abstinence (target n=270 per arm).

Missing outcome data. For secondary analyses, we will examine outcomes for all eligible screening patients who are current smokers offered screening by a participating randomized provider during the study period. This analysis will include patients who do not participate in the survey assessment of cessation outcomes. We will perform two secondary analyses. The first will assume that patients who do not participate in the survey assessment (e.g. missing abstinence outcomes) will be considered continued smokers, which is a typical intent-to-treat approach for cessation trials. We do not anticipate differential missing data across study arms. Second, we will address potential missing cessation data by requesting a HIPAA waiver and waiver of informed consent to review EMR data for all eligible patients to estimate an administrative assessment of cessation, based on HealthFactors data and whether patients report quitting at a subsequent visit or when they return for annual lung cancer screening. The methods developed by McGinnis et al, will be used to construct this administrative cessation variable.

(Note, due to COVID pandemic changes in lung cancer screening utilization and study enrollment timelines, the missing data protocol using EMR data was adapted for the primary outcome. See the Statistical Analysis Plan.)

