Current employment status	Self-report from screening and baseline questionnaires	Categorical	✓		
Service connection	EHR	Binary	✓		
¹ Months post-LCS					

		Assessment Timepoint			
Measure (Units)	Comments	Data Type	BL	3M ¹	12M ¹

7. Statistical Analyses and Description of Main Tables

Aim 1 statistical analyses

The primary analysis will be an intent-to-treat based comparison of the two intervention arms. The analysis will be performed at the level of the individual. Clustering of patients within providers will be accounted for in the analysis by the inclusion of a random intercept for provider. The primary analysis will be based on the following random intercept logistic regression model

$$\text{logit}^{-1} \left(P(Y_{ij} | Treatment, Site) \right) = \beta_0 + \alpha_j + \beta_1 Treatment + \beta_2 Site$$

Where Y_{ij} is an indicator variable for whether the i^{th} patient of the j^{th} provider had quit smoking at 12 months, *Treatment* is a binary indicator for assigned treatment arm, and *Site* is a binary indicator for VA medical center (New York Harbor or Providence). The α_j represent random intercepts for each provider and are assumed to follow a common $N(0, \sigma^2)$ distribution. We will report point estimates and 95% confidence intervals for the odds ratio $\exp(\beta_1)$. Confidence intervals will be computed using bootstrap methods. A test of the null hypothesis of no association ($\beta_1 = 0$) will be performed using a likelihood ratio test. A p-value of less than 0.05 will be taken as sufficient evidence to reject the null hypothesis of no association.

Analyses for secondary outcomes will use models with similar predictor terms but with different link functions depending on the outcome. The table below describes model types in more detail for each outcome.

Analysis	Description	Outcome	Independent Variable(s)	Model type	Statistical Test
Primary outcome	Smoking cessation at 12 months	Indicator of smoking abstinence at 12 months	Binary treatment indicator; Binary site indicator; Categorical provider	Logistic regression with random intercept for provider	

Analysis	Description	Outcome	Independent Variable(s)	Model type	Statistical Test
			(clustering variable)		

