			(clustering variable)		
Secondary outcome	Perceived susceptibility to lung cancer	Score on susceptibility scale	Binary treatment indicator; Binary site indicator; Categorical provider (clustering variable)	Linear regression with random intercept for provider	

8. Handling of Missing Data

In descriptive statistics, we will describe the extent of missing data. We will examine whether there is differential missingness in outcomes across treatment arms and sites. We will assess the extent to which the distributions of patient characteristics differ between those with the primary outcome and those without the primary outcome.

Patients may have missing data due to survey non-response or missing EHR data. The primary analysis will be a complete-case analysis among those who have a smoking status at 12 months. In sensitivity analyses, we will adapt a method to examine the impact of non-ignorable missingness on the study's primary conclusions. We will use the following model, which incorporates a Missing Not at Random (MNAR) missingness mechanism through a sensitivity parameter representing the odds ratio of smoking cessation between people with missing outcomes and people without missing outcomes.

$$\text{logit}^{-1}(P(\text{Smoking})) = \beta_0 + \beta_1 \text{Tx} + \beta_2 \text{Site} + \beta_3 \text{Missing}$$

9. Project Links

Clinical Trials Website:

<https://clinicaltrials.gov/ct2/show/NCT03612804>

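### The analysis called intent-to-treat is complete-case, and the SAP's MNAR model cannot show bias if early quitting is linked to having an observed outcome in one arm more than the other

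*SAP*

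**What the plan says.** Protocol section 5.6 promises: "We will utilize an intent-to-treat approach and include all participants who meet study eligibility criteria and are assigned to a study arm". The same paragraph then bases the primary analysis on participants with complete 12-month abstinence data, with a target of 270 per arm. SAP section 7 says "The primary analysis will be an intent-to-treat based comparison of the two intervention arms", and SAP section 8 says "The primary analysis will be a complete-case analysis among those who have a smoking status at 12 months".

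SAP section 7 lists these predictors for the primary model: "Binary treatment indicator; Binary site indicator; Categorical provider", the last entering as a random intercept. SAP section 5 builds the primary outcome from the 12-month survey and EMR data. A note in protocol section 5.6 says the EMR approach to missing data was adapted for the primary outcome because of the pandemic.

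For missing outcomes, SAP section 8 plans three things:
- a check of missingness by arm and site;
- a comparison of patient characteristics between those with and without the outcome;
- an MNAR model with terms for treatment, site and missingness.

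Three-month smoking appears in SAP section 7 only as a secondary outcome. Protocol section 5.6 also plans a secondary analysis of all eligible patients in which those without a survey outcome "will be considered continued smokers, which is a typical intent-to-treat approach for cessation trials". The SAP does not mention that analysis.

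**The concern.** An analysis of observed outcomes by assigned arm estimates the effect in all eligible patients only if, within arm and site, having an observed status is unrelated to quitting. People who quit early may be easier to reach or more willing to answer. The two arms are also handled differently: only proactive patients receive the notification letter and Quitline calls, and only their providers receive coordinator notes. It is therefore plausible that the link between quitting and being observed differs by arm.

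Protocol section 5.1 says CDW data are extracted for all invited patients, including survey non-responders, and a 3-month survey is sent to everyone eligible. The plan thus collects information on who is missing but uses none of it to correct the comparison. It goes straight from complete cases to an MNAR shift. At stake is whether a positive result could reflect who was observed rather than who quit.

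**Working it through.** **Planning figure.** Protocol section 5.2 says "We anticipate approaching up to 1,350 eligible potential subjects" and wants 540 completed 12-month surveys: 540/1,350 = 40%. This is survey completion only, with an upper limit as denominator. The share with a survey or EMR status will be higher, and the documents do not give it.

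**Assumptions (not in the documents).** Of patients abstinent at 3 months, q1 = 60% are abstinent at 12 months; of the others, q0 = 5%. Let p be 3-month abstinence, and r1 and r0 the chance of an observed 12-month status for 3-month quitters and for others. Clustering is ignored. Rejection rates use a two-sided 5% test of two proportions with 270 per arm.

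Complete-case rate = [p·r1·q1 + (1−p)·r0·q0] / [p·r1 + (1−p)·r0]

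**1. Similar link in both arms, true effect present** (p = 0.20 proactive, 0.10 unstructured)
- Truth: 0.20×0.60 + 0.80×0.05 = 16.0%; 0.10×0.60 + 0.90×0.05 = 10.5%. Difference 5.5 points, OR 1.62.
- About 40% observed (r1/r0 = 0.60/0.35 and 0.60/0.37): 0.0860/0.400 = 21.5%; 0.05265/0.393 = 13.4%. Difference 8.1 points, OR 1.77. With identical rates of 0.60/0.36 in both arms, OR 1.71.
- Higher observation (0.90/0.75 in both): 0.138/0.780 = 17.7%; 0.08775/0.765 = 11.5%. Difference 6.2 points, OR 1.66.
- With no true effect and the same link, the formula gives the same rate in both arms: OR 1.00, type I error 5%.

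**2. Link only in the proactive arm, no true effect** (p = 0.12 in both)
- Truth: 0.12×0.60 + 0.88×0.05 = 11.6% in both. In the unstructured arm observation is unrelated to quitting, so 11.6% is seen.
- Proactive at 0.60/0.37: (0.0432 + 0.01628)/(0.072 + 0.3256) = 0.05948/0.3976 = 15.0%. OR 1.34, rejection about 21%.
- Proactive at 0.90/0.75: (0.0648 + 0.0330)/(0.108 + 0.660) = 0.0978/0.768 = 12.7%. OR 1.11, rejection about 7% (8.5% with 500 per arm).

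**3. Would the planned checks show it?** Take the 15.0% versus 11.6% case, with the unstructured arm 40% observed.
- Missingness by arm: 39.8% versus 40.0% observed, so it looks balanced.
- MNAR model with a common missing-versus-observed odds ratio k. In each arm, missing rate = k·odds/(1 + k·odds), and overall rate = observed share × observed rate + missing share × missing rate.

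| k | proactive | unstructured | OR |
|---|---|---|---|
| near 0 (missing = smoking) | 5.9% | 4.6% | 1.30 |
| 0.2 | 8.0% | 6.2% | 1.32 |
| 0.5 | 10.8% | 8.3% | 1.33 |
| 1 | 15.0% | 11.6% | 1.34 |
| 2 | 21.6% | 17.1% | 1.34 |

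- The truth is 1.00. The true missing rate in the proactive arm is (0.116 − 0.05948)/(1 − 0.3976) = 9.4%, which is k = 0.59 there and k = 1 in the other arm. Only an arm-specific parameter reaches that point.

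**4. What auxiliary data would do.** If 3-month status were known for everyone and explained the missingness, imputation or weighting within arm gives 0.12×0.60 + 0.88×0.05 = 11.6% in both arms, OR 1.00.

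**5. Other assumptions** (50% and 4% in place of 60% and 5%; 9% true abstinence in both arms; link only in the proactive arm)
- 0.55/0.37 against 40%: OR 1.26, rejection 12.5%.
- 0.70/0.35 against 40%: OR 1.51, rejection 32%.
- 0.90/0.70 against 75%: OR 1.15, rejection 7.7%.
- With a true 9% versus 18% (OR 2.22), a link at 0.55/0.37 gives 2.87 if only in the proactive arm and 1.77 if only in the unstructured arm. The bias can go either way.

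**The case against.** Four points on the other side have force.

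- **Chart data are used.** A reader might infer that the plan ignores CDW data. It does not: EMR smoking status enters the primary outcome, and CDW characteristics are compared between patients with and without it. Only their use as auxiliary variables in an analysis is absent.
- **Not every link does harm.** A reader might infer that any association between early quitting and response biases the result. Step 1 shows otherwise for the null test and, largely, for the odds ratio, which is the SAP's effect measure. The risk difference moves more.
- **The label is partly terminology.** Protocol section 5.6 explains intent-to-treat as inclusion whatever care was taken up, and then openly states the restriction to complete outcomes. This stands as mitigation, but the two statements still describe different sets of patients.
- **Missing-equals-smoking has not been withdrawn.** It remains in the protocol, and the pandemic note concerns only EMR data. The SAP's silence is a gap between documents. By step 3 that analysis would not expose an arm-specific link either.

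Three-month status also comes from the same mail and telephone process, so it will be missing for some of the same patients. That limits the remedy, and is why EMR records and CDW variables belong in it.

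**Conclusion.** The point holds in a bounded form. The primary analysis is a complete-case analysis by assigned arm, and the SAP specifies no analysis that uses 3-month status or CDW characteristics to correct for non-response. A similar link in both arms is a minor matter. A link that differs by arm can bias both the estimate and the test. In the main illustration, false positives run from about 7% with about 77% of the proactive arm observed to about 20% at 40%. The higher figure should not be read as the expected error rate: it needs both an arm-specific link and survey-only observation. All these sizes rest on assumed quitting and response rates, without clustering.

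The firmest part does not depend on the exact rates. With a single missingness term and no missingness-by-treatment term, the MNAR model assumes away the arm-specific case and could give false reassurance. As printed it also lacks the provider intercept and gives no range for its parameter. This should be changed, but it does not invalidate the primary analysis.

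**What to change.** - Describe the primary analysis in both documents as a complete-case analysis by assigned arm.
- Prespecify a sensitivity analysis on all eligible patients: multiple imputation within arm with a provider effect, or inverse-probability weighting. Use 3-month smoking status where available, EMR smoking records and CDW baseline variables as auxiliary variables. Keep 3-month status out of the outcome model, because it arises after randomisation and may carry part of the treatment effect.
- Let the MNAR parameter differ by arm, add the provider intercept, and state the range to be examined.
- Carry the protocol's missing-equals-smoking analysis into the SAP, so that the two documents agree.

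The cost is SAP wording and analyst time on data the plan already collects. The drawbacks are reliance on an imputation or weighting model and limited information on patients who also miss the 3-month survey.
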